7.3 Subject Population(s) for Analysis

• All-completed population: All subjects that receive at least one dose will be considered for analysis.

Safety and Adverse Events 8

Definitions 8.1

Unanticipated Problems Involving Risk to Subjects or Others (UPIRTSO)

Any unanticipated problem or adverse event that meets the following three criteria:

- Serious: Serious problems or events that results in significant harm, (which may be physical, psychological, financial, social, economic, or legal) or increased risk for the subject or others (including individuals who are not research subjects). These include: (1) death; (2) life threatening adverse experience; (3) hospitalization - inpatient, new, or prolonged; (4) disability/incapacity - persistent or significant; (5) birth defect/anomaly; (6) breach of confidentiality and (7) other problems, events, or new information (i.e. publications, DSMB reports, interim findings, product labeling change) that in the opinion of the local investigator may adversely affect the rights, safety, or welfare of the subjects or others, or substantially compromise the research data, AND
- Unanticipated: (i.e. unexpected) problems or events are those that are not already described as potential risks in the protocol, consent document, not listed in the Investigator's Brochure, or not part of an underlying disease. A problem or event is "unanticipated" when it was unforeseeable at the time of its occurrence. A problem or event is "unanticipated" when it occurs at an increased frequency or at an increased severity than expected, AND
- Related: A problem or event is "related" if it is possibly related to the research procedures.

Adverse Event

An untoward or undesirable experience associated with the use of a medical product (i.e. drug, device, biologic) in a patient or research subject.

Serious Adverse Event

Adverse events are classified as serious or non-serious. Serious problems/events can be well defined and include;

- death
- life threatening adverse experience
- hospitalization
- inpatient, new, or prolonged; disability/incapacity
- persistent or significant disability or incapacity
- birth defect/anomaly

and/or per protocol may be problems/events that in the opinion of the sponsor-investigator may have adversely affected the rights, safety, or welfare of the subjects or others, or substantially compromised the research data.

events.

All adverse events that do not meet any of the criteria for serious, should be regarded as **non-serious adverse**

Adverse Event Reporting Period

For this study, the study treatment follow-up period is defined as 30 days following the last administration of study treatment.

Preexisting Condition

A preexisting condition is one that is present at the start of the study. A preexisting condition should be recorded as an adverse event if the frequency, intensity, or the character of the condition worsens during the study period.

General Physical Examination Findings

At screening, any clinically significant abnormality should be recorded as a preexisting condition. At the end of the study, any new clinically significant findings/abnormalities that meet the definition of an adverse event must also be recorded and documented as an adverse event.

A thorough baseline screening will be followed for all subjects and is outlined in Table-2. A detailed list of the methods in which baseline screening will be performed is outlined in Supplemental 2. All blood draws and safety assessments must be performed **prior** to study treatment administration. Appropriate safety assessments (e.g., evaluation of AEs and SAEs) should be repeated after dosing with study treatment. A physical examination, including general appearance and vital signs, will be performed as indicated in Table-2. If indicated, based on medical history and/or symptoms, additional exams will be performed at the discretion of the investigator. If possible, the same member of the study site staff throughout the study will perform assessments for an individual subject. Information for all physical examinations will be included in the source documentation at the study site. Significant findings that are present prior to the subject signing informed consent will be included in the Medical History. Significant findings made after the signing of the informed consent, which meet the definition of an AE, must be recorded as an AE. Vital signs (blood pressure, pulse, height, weight) will be assessed at each physical examination as indicated in Table-2 (see Supplemental 2 for details on how to acquire vital signs). Whether action needs to be taken to address notable vital signs will be decided by the investigator, considering the overall status of the subject.

Temporary Interruption of Investigational Product: In some circumstances, patients may need to temporarily interrupt treatment as a result of AEs or abnormal laboratory values that may have an unclear relationship to investigational product. For the abnormal laboratory findings and clinical events (regardless of relatedness), specific guidance is provided for temporarily interrupting treatment and when treatment may be restarted. Retest frequency and timing of follow up laboratory tests to monitor the abnormal finding is at the discretion of the investigator. Investigational product that was temporarily interrupted because of an AE or abnormal laboratory value may be restarted at the discretion of the investigator.

- Absolute Neutrophil Count (ANC): Treatment should be interrupted if ANC < 1 x 109 cells/L and may be restarted once ANC return above this value
- Absolute Lymphocyte Count (ALC): Treatment should be interrupted if ALC $< 0.5 \times 109 \text{ cells/L}$ and may be restarted once ALC return above this value
- Hemoglobin (Hb): Treatment should be interrupted if Hb < 8 g/dL and may be restarted once Hb return above this value
- Hepatic transaminases: Treatment should be temporarily interrupted if drug-induced liver injury is suspected

Permanent Discontinuation from Investigational Product: Investigational product must be permanently discontinued if the patient or the patient's designee requests to discontinue investigational product. Discontinuation of the investigational product for abnormal liver tests should be considered by the investigator when a patient meets 1 of the following conditions:

- ALT or AST >8 x ULN
- ALT or AST >5 x ULN for more than 2 weeks after temporary interruption of investigational product
- ALT or AST >3 x ULN and total bilirubin level (TBL) >2 x ULN or international normalized ratio (INR) >1.5
- ALT or AST >3 x ULN with the appearance of fatigue, nausea, vomiting, right upper quadrant pain or tenderness, fever, rash, and/or eosinophilia (>5%)
- ALP >3 x ULN that is deemed to be of liver origin and drug-related
- ALP >2.5 x ULN and TBL >2 x ULN
- ALP >2.5 x ULN with the appearance of fatigue, nausea, vomiting, right upper-quadrant pain or tenderness, fever, rash, and/or eosinophilia (>5%)
- Investigational product should be permanently discontinued if any of the following laboratory abnormalities are observed:
- White blood cell count $<1000 \text{ cells}/\Box L (1.00 \text{ x } 103/\Box L \text{ or } 1.00 \text{ billion}/L)$

- ANC <500 cells/ \Box L (0.50 x 103/ \Box L or 0.50 billion/L)
- Lymphocyte count <200 cells/□L (0.20 x 103/□L or 0.20 billion/L)
- Hemoglobin <6.5 g/dL (<65.0 g/L)

Hepatitis B virus DNA testing will be performed in enrolled patients who tested positive for HBcAb at screening. Patients who are HBcAb-positive and HBV DNA-negative (undetectable) at Visit 1 will require HBV DNA monitoring every 3 months and at the patient's last visit, regardless of their hepatitis B surface antibody (HBsAb) status. The following actions should be taken in response to HBV DNA test results:

- If a single result is obtained with a value "below limit of quantitation," the test should be repeated within approximately 2 weeks.
- If the repeat test result is "target not detected," monitoring may resume according to the study schedule.
- If the patient has 2 or more test results with a value "below limit of quantitation" during the study, HBV DNA testing should be performed approximately once per month for the remainder of the study and referral to a hepatologist is recommended.
- If a result is obtained with a value above limit of quantitation at any time during the study, the patient
 will be permanently discontinued from investigational product and should be referred to a hepatology
 specialist immediately

Supplemental 1: Appropriateness of Measures

Skin Scoring:

There are no validated skin scoring systems for LP. Therefore, we will use simple measures of BSA which is objective and PGA which is well validated in other inflammatory skin conditions. Additionally, we will simply annotate the number of lesions on the individual as a marker of total disease burden. The latter measure, mCAILS was devised for evaluation of cutaneous T-cell lymphoma lesions for trial purposes. This system provides accurate measurements of CTCL patches, plaques, and tumors. This scoring system captures lesion redness, size, texture, pigmentation and elevation characteristics. We will use a Modified CAILS scoring system that discards pigmentation scoring as resolving LP lesion inherently leave behind hyperpigmented skin changes which may confound active lesion scoring. This will provide a composite analysis of the index lesions as well as the general body involvement of the individual. The Modified CAILS system is advantageous over the PASI or EASI system in that in allows for more accurate calculation of surface area and incorporates that into the final score.

In cases where some or all of the affected body regions contain such extensive LP disease that make counting individual LP lesions unfeasible, the lesion count in these areas will be estimated. The palmar surface of the hand equates to approximately 1% BSA. To estimate the lesion count in a body region of extensive disease, the number of lesions counted within an area equivalent to area the palmar surface of the hand within that extensively diseased body region will be multiplied by the representative BSA of that body region to determine the estimated lesion count contained in that body region. Representative BSAs of body regions are defined as follows: head (7%), neck (2%), anterior trunk (13%), arms (8%), forearms (6%), hands (5%), posterior trunk (13%), buttocks (5%), thighs (19%), legs (14%), feet (7%) and groin (1%).

Itch Scoring:

The VAS, VRS, NRS and Skindex-16 are all well validated measure of itch. The VAS, VRS and NRS scores focus on a gestalt of itch. The Skindex-16 scoring system focuses on itch and its impact upon quality of life.

Supplemental 2: Safety Measures

Baseline Screening:

A serum β -hCG test will be performed in all pre-menopausal women as indicated. All pre-menopausal women who are not sterile at screening will also have a urine pregnancy test performed locally as indicated. Any woman with a confirmed positive pregnancy test during screening is not eligible for the study. A positive urine pregnancy test during the treatment periods of the study requires immediate interruption of study treatment until serum β -hCG is performed and found to be negative. If the serum β -hCG test is positive, study treatment must be definitively discontinued.

Blood Pressure and Pulse:

Height and Weight:

Height and body weight will be measured in indoor clothing, but without shoes. If possible, body weight assessments should be performed by the same study site staff member and using the same scale throughout the study.

Blood Draws:

Subjects should avoid smoking within the hour preceding the blood draws. All laboratory studies will be conducted within the Mayo Clinic Health Systems (Mayo Clinic Arizona and Mayo Clinic Rochester). Details on the collections, shipment of samples and reporting of results will follow Mayo Clinic's current protocols. For the identification of notable values, the Mayo Clinic reference laboratory should be consulted.

Supplemental 3: Safety Monitoring

Infection monitoring:

Study subjects will be evaluated at each visit for signs or symptoms of infection.

- Vitals signs as well as constitutional symptoms will be assessed.
- Assessment for common infections such as cellulitis as well as oral, vaginal, and cutaneous candidiasis will be performed

Post-study Adverse Event

All unresolved adverse events should be followed by the sponsor-investigator until the events are resolved, the subject is lost to follow-up, or the adverse event is otherwise explained. At the last scheduled visit, the sponsor-investigator should instruct each subject to report, to the sponsor-investigator, any subsequent event(s) that the subject, or the subject's personal physician, believes might reasonably be related to participation in this study.

Abnormal Laboratory Values

A clinical laboratory abnormality should be documented as an adverse event if

- they induce clinical signs or symptoms,
- they are considered clinically significant,
- they require therapy.

Laboratory studies will be drawn as indicated in Table-2. Whether action needs to be taken to address notable laboratory values will be decided by the investigator, considering the overall status of the subject. Hematology assessments will be measured at all scheduled study visits specified in Table-2. Serum chemistry will be a comprehensive metabolic panel will be measured at all scheduled study visits specified in Table-2.

Hospitalization, Prolonged Hospitalization or Surgery

Any adverse event that results in hospitalization or prolonged hospitalization should be documented and reported as a serious adverse event unless specifically instructed otherwise in this protocol. Any condition responsible for surgery should be documented as an adverse event if the condition meets the criteria for an adverse event.

Neither the condition, hospitalization, prolonged hospitalization, nor surgery are reported as an adverse event in the following circumstances:

• Hospitalization or prolonged hospitalization for diagnostic or elective surgical procedures for a preexisting condition. Surgery should **not** be reported as an outcome of an adverse event if the purpose of the surgery was elective or diagnostic and the outcome was uneventful.

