8.3 Reporting of Serious Adverse Events and Unanticipated Problems

When an adverse event has been identified, the study team will take appropriate action necessary to protect the study participant and then complete the Study Adverse Event Worksheet and log. The sponsor-investigator will evaluate the event and determine the necessary follow-up and reporting required.

Relationship of adverse events to study drug

For all AEs, the investigator will assess the causal relationship between the study drug and the AE using his/her clinical expertise and judgment according to the following algorithm that best fits the circumstances of the AE. The investigator will interpret and document whether or not an AE has a reasonable possibility of being related to study treatment, study device, or a study procedure, taking into account the disease, concomitant treatment or pathologies. A "reasonable possibility" means that there is a cause and effect relationship between the investigational product, study device and/or study procedure and the AE. The investigator answers yes/no when making this assessment.

Planned surgeries and nonsurgical interventions should not be reported as AEs unless the underlying medical condition has worsened during the course of the study.

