8.3.1 Sponsor-Investigator reporting: notifying the Mayo IRB

The sponsor-investigator will report to the Mayo IRB any UPIRTSOs and Non-UPIRTSOs according to the Mayo IRB Policy and Procedures.

Action taken regarding treatment

AE Action:

All adverse events should be treated appropriately. Treatment may include one or more of the following:

- No action taken (i.e. further observation only)
- [study/investigational] treatment dosage adjusted/temporarily interrupted
- [study/investigational] treatment permanently discontinued due to this adverse event
- concomitant medication given
- non-drug therapy given

• patient hospitalized/patient's hospitalization prolonged

AE Outcome:

• All AE outcomes should be recorded (not recovered/not resolved; recovered/resolved; recovering/resolving, recovered/resolved with sequelae; fatal; or unknown)

Serious Adverse Events (SAE)

An SAE is defined as any adverse event (appearance of (or worsening of any pre-existing) undesirable sign(s), symptom(s) or medical conditions(s) which meets any one of the following criteria (Life-threatening in the context of a SAE refers to a reaction in which the patient was at risk of death at the time of the reaction; it does not refer to a reaction that hypothetically might have caused death if more severe.):

- Is fatal or life-threatening
- Results in persistent or significant disability/incapacity
- Constitutes a congenital anomaly/birth defect
- Requires inpatient hospitalization or prolongation of existing hospitalization, unless hospitalization is for:
 - o Routine treatment or monitoring of the studied indication, not associated with any deterioration in condition (specify what this includes)
 - Elective or pre-planned treatment for a pre-existing condition that is unrelated to the indication under study and has not worsened since signing the informed consent
 - Treatment on an emergency outpatient basis for an event not fulfilling any of the definitions of a SAE given above and not resulting in hospital admission
 - O Social reasons and respite care in the absence of any deterioration in the patient's general condition
- Is medically significant, i.e. defined as an event that jeopardizes the patient or may require medical or surgical intervention.

SAE Reporting:

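### The section 8.1 exemption for elective or diagnostic admissions omits the not-worsened condition that sections 8.1, 8.3 and 8.3.1 state elsewhere, so one admission can be classified two ways

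*Combined protocol and SAP*

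**What the plan says.** The general rule in section 8.1 (Hospitalization, Prolonged Hospitalization or Surgery) is that an adverse event leading to admission "should be documented and reported as a serious adverse event unless specifically instructed otherwise in this protocol". An exemption follows. Its lead-in reads "Neither the condition, hospitalization, prolonged hospitalization, nor surgery are reported as an adverse event in the following circumstances", and the single circumstance listed is "Hospitalization or prolonged hospitalization for diagnostic or elective surgical procedures for a preexisting condition". The exemption names the condition as well as the admission and the surgery. It does not mention worsening or any relation to lichen planus (LP).

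Three other rules deal with the same situation:

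- **Section 8.1, Preexisting Condition:** a preexisting condition "should be recorded as an adverse event if the frequency, intensity, or the character of the condition worsens during the study period".
- **Section 8.3:** planned surgeries and nonsurgical interventions "should not be reported as AEs unless the underlying medical condition has worsened during the course of the study".
- **Section 8.3.1, Serious Adverse Events:** an elective or pre-planned admission falls outside the SAE definition only when it is for a "pre-existing condition that is unrelated to the indication under study and has not worsened since signing the informed consent".

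**The concern.** The exemption lacks the qualifier that the three other rules share, and the gap falls on the cases where a drug effect is in question. A stable condition treated electively is unlikely to be a safety signal. A condition that deteriorated on baricitinib and led to a procedure might be one.

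Such conditions can be present in the sample. Section 5.5 allows stable medication for chronic illness. The specific vascular criteria in section 4.2 exclude recurrent VTE, and VTE, myocardial infarction or unstable ischemic heart disease within 12 weeks of screening. They do not by themselves exclude a single older VTE or an older cardiac event.

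Safety is part of the stated objective in the Study Summary, and the trial has one arm of 12 subjects. The AE and SAE counts are the safety result, and related grade 3 or higher non-hematologic events feed the accrual rule in section 8.4. A classification rule that can be read two ways makes those counts depend on which paragraph the study team follows.

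**Working it through.** The plan states no figure on this point, so there is none to reproduce. The check sets the rules side by side.

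**Step 1. Four kinds of admission run through the rules.**

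| Admission | 8.1 exemption, read literally | 8.1 Preexisting Condition | 8.3 | 8.3.1 | Result |
|---|---|---|---|---|---|
| (a) Elective or diagnostic surgical; condition stable and unrelated to LP | Not reported | Not an AE | Exempt | Exempt | Rules agree |
| (b) Same kind of admission; condition worsened on study | Neither condition nor admission reported | AE | Exemption lost | Elective exception does not apply | **Conflict** |
| (c) Same kind of admission, for LP itself; not worsened | Not reported | Not an AE | Exempt if planned | Elective exception does not apply; the separate exception for routine treatment of the studied indication might | Possible mismatch |
| (d) Emergency or non-procedural; condition worsened | Outside the exemption | AE | Not a planned procedure | SAE | Rules agree; nothing lost |

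The definite conflict is (b). Case (c) is a secondary mismatch that comes from the unrelated-to-indication condition in 8.3.1.

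**Step 2. Does other text settle case (b)?**

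- The general hospitalization rule in 8.1 gives way where the protocol specifically instructs otherwise. The exemption can be read as such an instruction.
- The same sub-section says "Any condition responsible for surgery should be documented as an adverse event if the condition meets the criteria for an adverse event". That sentence comes just before the exemption. The exemption then names the condition, so it can be read as an exception to that sentence.
- Section 8.2 requires all adverse events to be recorded, and 8.3.1 requires every SAE to be reported whatever its cause. Both apply once something has been classed as an AE or SAE. The exemption acts on that classification.
- No passage says which rule prevails.

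Case (b) is therefore left open by the text.

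**Step 3. Size.** The documents give no rate of elective or diagnostic admissions, so no expected under-count can be calculated. The following shows sensitivity only.

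- One event among 12 subjects: 1/12 = 8.3 percentage points.
- Exact (Clopper-Pearson) 95% limits for 0/12: lower limit 0, upper limit 1 − 0.025^(1/12) = 26.5%.
- For 1/12: lower limit 1 − 0.975^(1/12) = 0.2%. The upper limit solves (1 − p)^12 + 12p(1 − p)^11 = 0.025, giving 38.5%.
- Section 8.4 suspends accrual at 2 or more of the first 6 treated patients. One unreported event would turn 2/6 into 1/6 only if it were grade 3 or higher, non-hematologic, at least possibly related and in one of the first six patients, and if exactly one other patient among those six already had a qualifying event.

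**The case against.** The strongest reply is that silence is not permission. The exemption does not say that worsened conditions are excluded. Read with the Preexisting Condition rule in the same section, the sentence on conditions responsible for surgery, the recording duty in 8.2 and the detailed SAE definition in 8.3.1, it can be taken to cover only a planned procedure for an unchanged condition. A careful investigator would probably record the worsening when it happened, before any admission. One might add that the exemption speaks of reporting and leaves recording alone. This is a fair way to harmonize the text, and it is why loss of events is a risk and not a finding. It does not remove the conflict: the reader has to supply a qualifier that the exemption lacks, and the SAE report for the admission stays in dispute even if the worsening is recorded.

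Several limits stand in full:

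- A reader might infer that the exemption reaches every admission for a preexisting condition. It does not. It covers diagnostic or elective surgical procedures only, and case (d) is untouched.
- It is unclear whether a non-surgical diagnostic test counts, because the word for diagnostic may or may not be tied to surgical. An admission for angiography would therefore be a debatable example.
- Section 4.2 also lets the investigator exclude subjects at unacceptable risk or with severe progressive or uncontrolled disease, which narrows the population concerned.
- Section 8.4 allows accrual to be suspended for unexpected event profiles that have not crossed the rule, so the numerical threshold is not the only safeguard.

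**Conclusion.** The point holds as an internal inconsistency of limited scope. For a preexisting condition that worsens on study and leads to a diagnostic or elective surgical admission, the 8.1 exemption read literally says not to report it. The other rules make the worsening an AE and withhold the exemption from the admission. The passages must be reconciled.

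A reader might infer that SAEs will be under-counted, or that such events can never reach SAE reporting. The documents do not support either inference. Loss occurs only if the exemption is applied literally and ahead of the other rules, and the frequency of such admissions is not given and is probably low. The one-in-12 and two-in-six figures show how much a single event would weigh. They are not forecasts, and section 7.2 plans descriptive summaries without naming an interval for the SAE proportion.

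The primary efficacy endpoint, PGA of skin at week 16, and its analysis are not affected. The change is still worth making because a stated rule, followed as written, contradicts three others on the cases that matter most for safety, and the missing condition already stands in the protocol.

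**What to change.** Amend the exemption in section 8.1 (Hospitalization, Prolonged Hospitalization or Surgery) so that it agrees with the Preexisting Condition rule in 8.1 and with 8.3 and 8.3.1:

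- Limit it to planned or elective procedures for a preexisting condition that has not worsened since informed consent.
- Align it with the unrelated-to-indication condition in 8.3.1, and say how an elective admission for LP itself is classed.
- State that a preexisting condition that has worsened remains an AE, and is an SAE if it results in hospitalization, including admission for diagnostic work-up.

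This takes a sentence or two in one section, with no new data or procedures. The downside is at most a few more SAE reports.
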